9.2.3.1 Action Taken

Action taken will be defined as:

- None;
- Clinical management of the AE;
- Dosing stopped.

9.2.3.2 Outcome

Outcome will be defined as:

- Resolved;
- Ongoing;
- Lost to follow up.

9.3 Recording and reporting of SAEs and SUSARs

The expectedness of the SAEs in relation to the IMP will be determined using the IB.

SAEs occurring on this study will be reported to the Sponsor Pharmacovigilance provider (PRA Health Sciences) and the Sponsor's medical representative within 24 hours of discovery or notification of the event. For contact details refer to the Key trial contacts section in this protocol. The Investigator will be requested to complete a separate SAE reporting form in addition to the information on the eCRF.

A SUSAR that is fatal or life-threatening must be reported to the CA and EC immediately (within 7 days) after the Sponsor becomes aware of the event. Any additional information must be reported within 8 days of sending the first report.

A SUSAR which is not fatal or life-threatening must be reported to the CA and EC according to country specific requirements after the Sponsor becomes aware of the event.

9.4 Responsibilities

Principal Investigator (PI):

- Checking for AEs when participants attend for treatment / follow-up and ensuring that all AEs are recorded.
- Using medical judgement in assigning seriousness and causality and providing an opinion on expectedness using the IB approved for the trial.
- Ensuring that all SAEs are recorded and reported to the Sponsor within 24 hours of becoming aware of the event and provide further follow-up information as soon as available. Ensuring that SAEs are followed up with Sponsor if a record of receipt is not received within 2 working days of initial reporting.

Chief Investigator (CI) or delegate:

- Clinical oversight of the safety of patients participating in the trial, including an ongoing review of the risk / benefit.
- Using medical judgement in assigning seriousness and causality where it has not been possible to obtain local medical assessment.
- Immediate review of all SUSARs, if the study is unblinded.
- Review of specific SAEs in accordance with the trial risk assessment and protocol as detailed in the Trial Monitoring Plan.
- Assisting in assigning Medical Dictionary for Regulatory Activities (MedDRA) or Body System coding to all SAEs and SARs.

Sponsor or delegate:

- Central data collection and verification of AEs, ARs, SAEs, SARs and SUSARs according to the trial protocol.
- Reporting safety information to the CI, delegate or independent clinical reviewer for the ongoing assessment of the risk / benefit according to the Pharmacovigilance Plan.
- Reporting safety information to the SRC according to the Trial Monitoring Plan.
- Expedited reporting of SUSARs to the CAs and ECs within required timelines.
- Assigning expectedness.
- Notifying Investigators of SUSARs that occur within the trial, if the study is unblinded.
- The unblinding of a participant for the purpose of expedited SUSAR reporting.
- Checking for (annually) and notifying PIs of updates to the IB for the trial.
- Preparing standard tables and other relevant information for the development safety update report (DSUR) in collaboration with the CI
- Assigning MedDRA or Body System coding to all SAEs in consultation with the CI or delegate.

Safety review committee (SRC)

- The SRC will review safety data from a sentinel group of each cohort before commencement to the remaining cohort. In addition, the SRC will review safety data after two injections in each cohort, prior to progression from Cohort 1 to Cohort 2, and prior to progression from Cohort 2 to 3.
- For review of data from the sentinel group, the SRC will consist of the PI(s) from the site(s) involved with sentinel dosing, the CI and the Sponsor's medical advisor.
- For review of data to allow progression between cohorts the SRC will consist of the CI, all PIs and the Sponsor's medical advisor. In addition, representative(s) from the Sponsor, or their delegate, may attend but without voting rights.

9.5 Notification of deaths

Any untoward medical occurrence resulting in death fulfils the definition of an SAE and is subject to expedited reporting as described in Section 9.3.

9.6 Pregnancy reporting

All pregnancies within the trial (either the trial participant or the participant's partner) should be reported to the Sponsor's Pharmacovigilance provider (PRA Health Sciences) in the first instance using the relevant Pregnancy Reporting Form for follow up and the Clinical Lead and the Medical Monitor should also be notified.

Pregnancy is not considered an AE unless a negative or consequential outcome is recorded for the mother or child/foetus. If the outcome meets the serious criteria, this would be considered an SAE.

If a subject is confirmed to be pregnant, use of the IMP will be discontinued immediately, however, the subject may continue with study follow up at the discretion of the investigator and obstetrician. The Investigator must provide follow-up information about the course of the pregnancy and outcome.

9.7 Overdose

An overdose is not expected, as the IMP is administered via IM injection. Should subjects allocated to the low dose of the IMP receive a higher dose than the allocated dose this should be reported in the eCRF and the Sponsor should be informed. Any deviations from the assigned dose will be handled as a protocol deviation.

9.8 Reporting urgent safety measures

If any urgent safety measures are taken the CI/Sponsor shall immediately and in any event no later than 3 days from the date the measures are taken, give written notice to the CAs and the relevant ECs of the measures taken and the circumstances giving rise to those measures.

9.9 The type and duration of the follow-up of subjects after adverse events

The Investigator will initiate appropriate treatment according to his/her medical judgment and will decide whether to discontinue dosing if an AE or a concurrent health condition occurs.

The subject may be followed up by additional examinations according to the medical judgment of the Investigator and the nature of the AE, until the abnormal condition is resolved or the Investigator deems further observations or examinations to be no longer medically indicated.

Any SUSAR will need to be reported to the Sponsor irrespective of how long after IMP administration the reaction has occurred.

10 STATISTICS AND DATA ANALYSIS

10.1 Treatment Arms

There are six treatment arms:

1. Low-dose FP-02.2 (Cohort 1)
2. High-dose FP-02.2 (Cohort 2)
3. Low-dose FP-02.2 + adjuvant (IC31®) (Cohort 2)
4. High-dose FP-02.2 + adjuvant (IC31®) (Cohort 3)
5. Placebo (pooled Placebo subjects)
6. IC31® only (pooled IC31® subjects)

10.2 Sample size calculation

No formal sample size calculation has been performed. It is planned to randomise approximately 10 subjects into each of the six treatment arms, which is considered an appropriate study size at this phase of development of Vaccine FP-02.2.

10.3 Statistical analysis plan

The proposed statistical analyses for this study will be detailed in a separate statistical analysis plan (SAP), which will be finalised prior to database lock. Any changes to the statistical analysis described in this protocol do not require a protocol amendment but must be described as a 'change to the protocol planned statistical analysis' in the SAP and the clinical study report.

The statistical analysis and report will conform to the relevant ICH requirements.

Data listings and summary tables will be generated using the software SAS® Version 9.3 or later. All data recorded in the eCRFs will be included in data listings. The SAS datasets and programs will be made available to the Sponsor at study closure.

Summary tables and data listings will be presented by treatment arm and time point.

The standard summary statistics for continuous variables will comprise number of valid observations, arithmetic mean, standard deviation, median, quartiles, minimum, and maximum. The geometric mean and coefficient of variation will also be presented for continuous variables which are positive and substantively positively skewed (such as liver enzyme levels, ELISpot counts and measures of viral load). The standard summary statistics for categorical data will comprise absolute and relative frequencies (proportions).

If continuous variables are assessed both at and after baseline, change from baseline will be calculated and summarised. If categorical variables are assessed both at and after baseline, then cross-tabulations will be presented by category at baseline.

10.4 Analysis Sets

Membership of analysis sets will be determined at a blinded data review meeting convened by the Sponsor.

10.4.1 Safety Analysis Set

The safety analysis set will contain all subjects who were randomised and received at least 1 injection of Vaccine FP-02.2, Vaccine FP-02.2/IC31®, placebo or IC31®.

10.4.2 Full Analysis Set (FAS)

The FAS comprises of all members of the safety analysis set with at least one complete post-vaccination immunogenicity result.

10.4.3 Immunogenicity Analysis Set

The immunogenicity analysis set comprises of all members of the FAS with immunogenicity assessments at screening followed by days 1, 8, 29, 36, 57, 64 and 85 and with no major protocol violations. Subjects with missing day 1 PBMC may be included if screening PBMC data are available to calculate a baseline.

10.5 Baseline data

Baseline data will be tabulated using the standard summary statistics over all randomised subjects.

10.6 Procedure(s) to account for missing or spurious data

There will be no imputation for missing data. Summaries will be over all valid cases at that time point in the applicable analysis set.

The nature and extent of missing data or spurious data will be reviewed at a blinded data review meeting.

10.7 Subject Disposition and flow of patients

Subject disposition tabulation will display number of patients screened and randomised, number of subjects in each analysis population, and having completed or withdrawn, as well as reasons for withdrawal/drop-out.

A subject will be considered enrolled at the time of randomisation. Subjects will be considered to have completed the study if they have taken all of the scheduled doses of IMP and have completed all applicable safety assessments and other study-related procedures.

The disposition table will be detailed enough to enable construction of a CONSORT-style flow diagram.

10.8 Study Conduct

10.8.1 IMP and NUC exposure

IMP and NUC exposure will be tabulated using the standard summary statistics.

10.8.2 Protocol Violations

Protocol violations will be listed and tabulated using the standard summary statistics. Violations with the potential for compromising the integrity or interpretation of the study will be referred to as 'major', other violations will be referred to as 'minor'. Whether or not each protocol deviation is categorised as 'major' will be determined at a blinded data review meeting convened by the Sponsor.

10.9 Safety analysis

Safety data in general will be listed and summarised by treatment arm and time point using the standard summary statistics over the safety analysis set.

10.9.1 Liver function

Liver function test results will be presented using the standard summary statistics and shift tables.

10.9.2 Adverse Events

Adverse events shall be coded according to the current version of MedDRA.

The subject incidence, severity, duration, relatedness and outcome of all treatment emergent AEs will be tabulated by treatment arm, system organ class and preferred term. Separate tables will be provided for fatal events, events leading to withdrawal, serious events and SUSARs.

Treatment emergent AEs will be flagged in the subject data listings.

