9.2 Operational definitions for (S)AEs

The occurrence of AEs will be assessed by non-directive questioning of the subject at each visit. Additionally, AEs volunteered by the subject during or between visits or detected through observation, physical examination, laboratory test or other assessments will be documented. Subjects will be instructed that they must immediately report any AEs, subjective complaints or objective changes in their well-being to the Investigator or the clinic personnel, regardless of the perceived relationship between event and test product.

All AEs must be fully recorded throughout the entire study period (from Screening Visit to Day 85) and will be entered into the subjects' eCRF, whether or not they are considered to be drug-related. Each AE should be described in detail: onset time and date, offset time and date, description of event, severity, relationship, action taken and outcome. From Day 85 and Day 225 only SAEs and AESIs will be collected.

Adverse events should be followed until recovery to the normal state has been achieved. In the event of a subject not returning to the clinical unit, every attempt will be made to contact the subject up to Day 85 after which the outcome of this event will be recorded as lost at follow-up.

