#### 12.6.1 Adverse Events

Adverse events will be coded using Version 20.0 or newer of MedDRA.

Treatment-emergent adverse events (TEAEs) are those which first occur or increase in severity or relationship probability to investigational product after the first dose of investigational product through 30 days after last dose of investigational product. Note that SAEs and AESIs are collected through 6 months after last dose of investigational product; therefore, all SAEs and AESIs will be summarized, not just treatment-emergent events.

All AEs which change in severity or relationship to investigational product are assigned a new start date and captured as a new record.

If more than 1 AE with the same preferred term is reported before the date of the dose of investigational product, then the AE with the greatest severity will be used as the benchmark for comparison to the AEs occurring during the study under the preferred term.

An overall summary of TEAEs, including the number and percentage of subjects who experience, and absolute count of treatment-emergent events for:

- Any TEAE
- Any TEAE by maximum severity
- Any TEAE considered possibly related to investigational product (defined as CRF response of "Reasonable Possibility")
- Any TEAE considered possibly related to investigational product by maximum severity
- Any SAEs
- Any SAEs considered possibly related to investigational product
- Any AEs with outcome of death
- Any AESIs (Hepatic flares and autoimmune conditions)
- Any TEAE leading to discontinuation of investigational product

The number and percentage of subjects reporting TEAEs, SAEs, or AESIs will be tabulated in the following ways by treatment group.

- By SOC and preferred term (including absolute count of events).
- By SOC, preferred term and maximum severity.
- By SOC and preferred term for TEAEs possibly related to investigational product in the opinion of the investigator (including absolute count of events).
- By SOC and preferred term for SAEs (including absolute count of events).
- By SOC and preferred term for possibly related SAEs (including absolute count of events).
- By SOC and preferred term for TEAEs leading to discontinuation of investigational product (including absolute count of events).
- By SOC and preferred term for AEs with fatal outcome (including absolute count of events).
- By SOC and preferred term for AESIs (including absolute count of events).

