Adverse events of special interest will be identified from the existing study AEs by medical review prior to database lock.

All AEs will be listed by subject. Separate listings will be provided for SAEs, AEs related to investigational product, AEs leading to discontinuation of investigational product, AEs with fatal outcome and suspected unexpected SAEs.

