### 14.3 Missing Date and Time Information for Adverse Events

For AEs, only incomplete (i.e., partially missing) start dates and times will be imputed.

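### The SAP drops the protocol's tables of TEAE duration, non-fatal TEAE outcome and SUSARs without declaring the change, and Appendix 1 omits the SUSAR listing that SAP 12.6.1 promises

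*Protocol*

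**What the plan says.** Protocol 10.9.2, repeated in the trial summary, names five attributes: "The subject incidence, severity, duration, relatedness and outcome of all treatment emergent AEs will be tabulated by treatment arm", with SOC and preferred term as the further breakdown. It adds: "Separate tables will be provided for fatal events, events leading to withdrawal, serious events and SUSARs".

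The data exist. Protocol 9.2 has each AE recorded with "onset time and date, offset time and date, description of event, severity, relationship, action taken and outcome". In protocol 9.2.3.2, "Outcome will be defined as" resolved, ongoing or lost to follow up.

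SAP 12.6.1 introduces its tables with "The number and percentage of subjects reporting TEAEs, SAEs, or AESIs will be tabulated in the following ways by treatment group". The list that follows covers incidence, maximum severity, relatedness, SAEs, related SAEs, discontinuation of product, fatal outcome and AESIs. The same section promises separate listings, the last of them being "AEs with fatal outcome and suspected unexpected SAEs". On dates, SAP 14.3 says "For AEs, only incomplete (i.e., partially missing) start dates and times will be imputed".

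On departures from the protocol, protocol 10.3 says "Any changes to the statistical analysis described in this protocol do not require a protocol amendment but must be described as a" change to the planned analysis, in both the SAP and the clinical study report. SAP 4.1 declares two changes: physical examinations are listed only, and the Immunogenicity Analysis Set is redefined.

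**The concern.** Safety and tolerability is the primary objective, and the Day 85 analysis is meant to inform formulation and dose for the next study (protocol 10.11, SAP 10.2). In the SAP's TEAE tables a two-day event and an event still present at Day 85 each count as one subject with an event. The protocol asked for duration and outcome, which are what would separate the two.

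This matters most for systemic events. The solicited reactions in protocol 7.6.1.7 are all local, while protocol 2.1.2 says that fever, malaise or body aches may occur. Such events enter as ordinary AEs, so how long they last and whether they resolve would show mainly through AE duration and outcome. The AESI table likewise carries neither.

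There is also a question of process: an analysis specified in the protocol for the primary endpoint disappears with no record that anyone decided to drop it.

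**Working it through.** No figure is in dispute, so the check compares the documents item by item.

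| Protocol 10.9.2 item | Where the SAP covers it | Result |
|---|---|---|
| Incidence | Tables 14.3.2.1, 14.3.2.2 | covered |
| Severity | Tables 14.3.2.3, 14.3.2.7 | covered |
| Relatedness | Tables 14.3.2.5 to 14.3.2.7 | covered |
| Duration | none | absent |
| Outcome | death line in the overall summary; Table 14.3.2.9 | fatal only |
| Separate table: fatal | Table 14.3.2.9 | covered |
| Separate table: withdrawal | Table 14.3.2.8 (discontinuation of product) | covered |
| Separate table: serious | Table 14.3.2.4 | covered |
| Separate table: SUSARs | none; nearest is Table 14.3.2.6 | absent |

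- **Attributes.** 3 of 5 are tabulated in full. Duration is absent. Outcome appears only as death, which meets the separate fatal-events requirement but tabulates none of the three categories in protocol 9.2.3.2.
- **Separate tables.** 3 of 4 are present. Table 14.3.2.6 (serious, possibly related) is the wider set that would contain any SUSAR, but it is not split by expectedness.
- **Listings.** SAP 12.6.1 promises five separate AE listings. Appendix 1 carries four of them (16.2.7.2 to 16.2.7.5) and adds one for AESIs (16.2.7.6). The SUSAR listing is missing, so the SAP disagrees with itself as well as with the protocol.
- **Declaration.** Of three gaps (duration, non-fatal outcome, SUSAR table), SAP 4.1 declares 0. One of the two changes it does declare moves physical examination from a summary to a listing. The SAP therefore already treats a change of that kind as one to declare.
- **Can duration be computed under the SAP's rules?** Not fully. SAP 14.3.1 refers only to the start-date and start-time rules, so a partial AE stop date has no rule. SAP 12.6.1 opens a new record when severity or relationship changes, and no rule links the pieces of one event. SAP 10.2 cuts each subject's data at Day 85 without saying how an event ongoing at the cut is shown.

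On granularity: in an arm of 10, one subject is 1/10 = 10 percentage points. That is the step size of any such table, not an estimate of how many subjects would have unresolved events. The documents give no AE rates from which to estimate that.

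**The case against.** A reader might infer that the SAP tabulates nothing on outcome, or that arms with long or unresolved reactions will look the same as arms with brief ones. The documents do not support either reading.

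- Fatal outcome is tabulated twice, in the overall summary and by SOC and preferred term.
- Injection-site reactions are tabulated by arm, severity and time point, from investigator assessment and from diary cards to day 7 (SAP 12.6.2, Tables 14.3.6.2 to 14.3.6.5). Local persistence over that week is visible.
- Laboratory values, including ALT, bilirubin and INR, are to be summarised with shifts from baseline at each time point (SAP 12.6.3).
- The data are not lost. Protocol 10.3 has all eCRF data listed, and SAP 12.6.1 lists all AEs by subject. With about 10 subjects per arm and no hypothesis tests, unresolved events can be counted by hand.
- Any SUSAR would appear in Table 14.3.2.6 and in the SAE listing; only the expectedness split is lost.
- Neither document says that AE duration or resolution drives the dose decision, and the primary analysis includes listings as well as tables.
- Protocol 10.3 lets the sponsor change the analysis without an amendment, so declaring the omission would be compliant.

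All of this stands, and it sets the limits of the point. It does not close the gap. The SAP does not itself say that the AE listing shows stop date or outcome, a listing is not the by-arm table the protocol specifies, and the declaration that would make the change compliant was not made.

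**Conclusion.** The point holds as an undeclared conflict between protocol and SAP on the primary safety endpoint. Duration and non-fatal outcome of TEAEs and the SUSAR table are required by the protocol and absent from the SAP, and the promised SUSAR listing is absent from Appendix 1.

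The consequence is limited. For events other than solicited local reactions, persistence and resolution cannot be compared by arm from the AE summary tables; they must be counted from the subject listings. This assumes that the AE listing will show stop date and outcome, as protocol 10.3 implies. If it does not, the information would not be reported at all for those events.

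The number of subjects affected cannot be estimated from the documents. The gap should be corrected in the SAP before database lock; it does not threaten the trial's conclusions as a whole.

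**What to change.** Add to SAP 12.6.1 and Appendix 1:

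1. TEAEs by arm, SOC, preferred term and outcome (resolved, ongoing, lost to follow up), with the number and percentage of subjects who have any TEAE ongoing at Day 85.
2. A descriptive summary of TEAE duration by arm. Count ongoing events separately or show them as censored at Day 85. Extend this to Day 225 only for SAEs and AESIs, because protocol 9.2 ends ordinary AE collection at Day 85. State a rule for partial AE stop dates, and link records split by a change in severity or relationship. The medication rules in SAP 14.2.2 are not a ready substitute: they set a fully missing stop date to the date of last dose, which would close an ongoing event.
3. The SUSAR table, and the SUSAR listing already promised in SAP 12.6.1.

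Any of these outputs that the sponsor chooses not to produce must be declared in SAP 4.1 and the clinical study report.

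The cost is a few extra descriptive outputs from fields already collected, plus a stop-date rule and a record-linking rule to write and program.
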